In recent systematic reviews, the existing evidence on the effectiveness of cannabinoids for chronic non-cancer pain, including fibromyalgia has been assessed, but only low-quality evidence has shown improved sleep and patient global impression of change and otherwise inconstant findings for the effect of medical cannabis for patients with fibromyalgia. Surveys have showed favorable effects on fibromyalgia symptoms, health-related quality of life, and improved pain management and sleep, among users of unlicensed cannabis compared to non-users. A recent retrospective study showed significantly favorable outcomes on fibromyalgia symptoms among medical cannabis users, and only mild adverse events. However, the designs in these studies, i.e., the relatively small sample size and short duration reduced the quality of the studies. Thus, based on the high demand and an increasing popularity of medical cannabis – currently used unlicensed among many patients with fibromyalgia, despite the lack of high-quality evidence on efficacy and safety, a well-designed randomized trial with a large sample size and clinically relevant trial duration is warranted. In this RCT we investigate the efficacy and safety of Cannabidiol (CBD) 50 mg for treating patients with fibromyalgia. We will explore the effect of CBD on pain intensity and other key symptoms associated with fibromyalgia.

Aim and Objective(s)

The aim of this trial is to investigate whether treatment with CBD is safe and has a superior effect compared to placebo on relevant outcomes in patients with fibromyalgia. The primary objective is to assess the effect of CBD 50 mg compared to placebo, on change in pain intensity (FIQ-R) from baseline to week 24. Key secondary objectives include assessing the effectiveness of CBD compared to placebo on changes in sleep quality, sleep duration, objectively measured sleep duration, objectively measured sleep patterns, Activities of daily living, Health-related quality of life, and energy level.

METHODS

Trial design

The CANNFIB trial was designed as a single-center, randomized, placebo-controlled, double-blind, parallel-group trial. Participants were randomized in a 1:1 manner to receive either cannabidiol 50 mg or placebo. Allocation was stratified based on sex (male vs. female), age (<45 vs. \geq 45 years at enrolment) and pain intensity (over vs. under 7 on the FIQ-R pain numeric rating scale), to ensure that the two groups are as alike as possible.

Framework

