The CONSORT flow diagram (Figure 1), includes information about the number of people recruited, screened, eligible, consented, randomized, allocated to treatment, withdrawal from treatment and lost to follow-up from baseline to week 36.

Withdrawals and follow-up

The CONSORT flow diagram (Figure 1) displays the number of participants lost to follow-up for the following time points; week 4 visit, week 12 visit, week 20 visit, week 24 visit (primary endpoint assessment), and week 36 visit. The reason for loss to follow-up will be reported as either due to adverse event or due to other reasons. The level of withdrawal will be categorized as withdrawal from the intervention, withdrawal from follow-up, or complete withdrawal.

Baseline characteristics

Baseline characteristics for each treatment arm will be summarized to visualize whether relevant demographic, pain-related, and other relevant characteristics appear balanced across the two groups. These data will be presented in the primary manuscript as shown in Table 1. Categorical data will be described using numbers and percentages. Normally distributed continuous data will be described using means and standard deviations (SDs), whereas continuous data that appear skewed will be described using medians and interquartile ranges.

Analysis

Outcome measures

A clinical trial's endpoints measure the outcomes in the trial. The following outcomes are applied in this study assessed 24 weeks from baseline.

Primary endpoint

Change in the pain intensity subscale of the Fibromyalgia Impact Questionnaire Revised (FIQ-R) from baseline to week 24.

Key secondary outcomes

Changes from baseline to week 24

- Sleep quality measured with the Pittsburgh Sleep Quality Index, total score of overall sleep quality. Scores are ranging from 0 to 21, with lower scores indicating better sleep quality and higher scores indicating worse sleep quality.
- Sleep duration measured with the Pittsburgh Sleep Quality Index, sleep duration domain, with number of hours of actual sleep during the night.
- Objectively measured sleep duration with number of minutes of nightly rest, measured with the Sens triaxial accelerometer device; MOTION® activity and rest measurement system.
- Objectively measured sleep patterns measured with the Sens triaxial accelerometer device; MOTION® activity and rest measurement system, in which movements during the night the number of times getting up during the night are indicated.

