- Change in sleep duration: assessed by the PSQI, sleep duration domain
- objectively measured sleep duration: assessed by the triaxial accelerometer device SENS MOTION®

- objectively measured sleep patterns: assessed by the triaxial accelerometer device SENS MOTION®
- Change in activities of daily living: assessed by AMPS ADL motor and ADL process ability measures, and ADL-Q total
- Change in Quality of life: assessed by the EQ5D total
- Change in energy level: assessed by the FIQ-R energy subscale

Finally, another secondary objective is to investigate the number of responders in both treatment groups. The following two responder categories are defined:

- Number of responders with 30 % improvement of the primary outcome
- Number of responders with 50 % improvement of the primary outcome

Analysis methods

The pre-specified efficacy analyses are based on the ITT population, which include all participants randomized and assessed at baseline. By applying repeated measures, mixed effects models for the continuous outcome measures, we assume that missingness (among the outcomes), is independent of unobserved measurements but dependent on the observed measurements i.e., assuming that data is '*Missing At Random*' (MAR). Reasonably valid estimates of treatment effects can be obtained using mixed models, even when the missing values are not completely random and additional methods for handling missing data, such as multiple imputation, are generally not required (7).

Our main analyses estimate between group differences for the continuous outcomes after 24 weeks of treatment for primary and key secondary outcomes. Repeated measurements at week 0, 4, 12, 20, 24 and the (12-week) follow-up at 36 weeks from baseline, will be analyzed based on linear mixed-effects models. All between-groups differences will be adjusted for baseline level to reduce random variation. The primary statistical model consists of fixed effect factors for design variables and random effects for patients. Fixed effects factors define the expected values of the observations, and random effects define the variance and covariances of the observations: Group, Stratification variable 1 (sex), Stratification variable 2 (age group), and Stratification

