variable 3 (severe pain intensity). Observations are made at 6 timepoints for the primary outcome measure (at baseline, 4, 12, 20, 24 and 36 weeks from baseline). Basically, there are two fixed-effect factors: group, time, and the interaction between as well as the three stratifying factors. Random effects result from variation between and within participants. While observations on different participants will be assumed to be independent, we anticipate that measures on the same patient at different times are correlated, with measures taken closely together in time being more highly correlated than measures taken more apart in time (8).

Secondarily an analysis of number of responders (dichotomous outcomes) in the two groups will be carried out. A responder was defined as a participant who reports a more than one FIQ-R unit, 30%, and 50% improvement in pain after 24 weeks of treatment with either CBD or placebo. For these dichotomous outcomes, we will calculate the Risk Ratio (RR) with 95 % CI comparing the two groups. For subsequent ease of interpretation, the RR values might be converted into Risk Differences (RD) and Number Needed to Treat (RD).

Missing Data

Repeated measure using mixed-effects models is based on the ITT population handle missing data indirectly, statistically modeled using repeated-measures linear mixed models (see below). These models will be valid if data are Missing at Random (MAR): *“Any systematic difference between the missing values and the observed values can be explained by differences in the observed data”* (7). Contrasts between groups will be estimated on least squares means derived from the mixed linear models (i.e., primary contrast at 24 weeks from baseline). The main analyses for the dichotomous outcomes will be based on a simple, single-step non-responder imputation in the case of any missing binary outcomes after 24 weeks.

Sensitivity analyses will be performed subsequently to confirm the robustness of the findings, including the following:

- Non-responder imputation: use of a simple single imputation technique where the baseline observation is carried forward. This approach is potentially informative if even if data are Missing Not At Random (MNAR) (9, 10)

- ‘Per Protocol’ population: defined as participants who have been compliant with the schedule of activities and has ingested the project medication throughout the study at the highest tolerated level.

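### The primary mixed model counts week 0 as a response and also adjusts for baseline; if both are fitted, the week-24 test is either liberal (about 6–9%) or loses the adjustment, depending on an unnamed covariance

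*SAP*

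**What the plan says.** The SAP's Analysis methods section puts week 0 among the modelled data: "Repeated measurements at week 0, 4, 12, 20, 24 and the (12-week) follow-up at 36 weeks from baseline, will be analyzed". It repeats this while describing the model: "Observations are made at 6 timepoints for the primary outcome measure (at baseline, 4, 12, 20, 24 and 36 weeks from baseline". The same section promises that "All between-groups differences will be adjusted for baseline level to reduce random variation". Protocol section 12.2 (version 4) says that baseline level enters as a covariate.

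The SAP's list of effects does not contain the baseline value: "Basically, there are two fixed-effect factors: group, time, and the interaction between as well as the three stratifying factors". One listed factor, "variable 3 (severe pain intensity", is defined under Trial design as "pain intensity (over vs. under 7 on the FIQ-R pain numeric rating scale".

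On covariance, the SAP mentions random effects for patients and expects correlation to fall as visits lie further apart. It names no structure. The Missing Data section takes the test from "least squares means derived from the mixed linear models (i.e., primary contrast at 24 weeks from baseline". The primary endpoint is worded as a change: "Change in the pain intensity subscale of the Fibromyalgia Impact Questionnaire Revised (FIQ-R) from baseline to week 24".

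**The concern.** A patient's week-0 value cannot serve both as an outcome and as its own predictor without consequences. At week 0 the covariate equals the response, so the residual is (1 − slope) × baseline, up to centring. This is artificially small and says nothing about treatment. A covariance that pools variance over visits takes in those small residuals, and the week-24 standard error falls. A covariance with a separate week-0 variance lets the fit make that residual vanish.

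This model supplies the one P-value that decides the primary hypothesis, and the intervals in Table 2. Its error rate and precision should not depend on a choice left to the programmer.

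**Working it through.** **Inputs.** From the SAP: SD 2, 100 per arm, two-sided 5%, three stratification factors, permuted blocks of up to 8 (8 used here), visits at weeks 0, 4, 12, 20, 24 and 36. Assumed, because the documents give no values: 10% male, 50% aged 45 or over, and three correlation patterns:
- (a) 0.85·exp(−lag/45), so the week 0–24 correlation is 0.85·exp(−24/45) = 0.50;
- (b) 0.80·exp(−lag/30), giving 0.36;
- (c) 0.5 at every lag.

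**The plan's own figure.** For the t-test, SE = 2·√(2/100) = 0.283. For 1 unit the noncentral t gives 94.0% power with 200 patients and 80.1% with 128. Both match the SAP.

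**Mechanism by hand.** Take correlation 0.5, ignore the strata, and use a fitted common slope of 0.58 (the week-0 rows pull it up from 0.50).
- Week-0 residual variance: (1 − 0.58)²·4 = 0.71.
- Variance at each later visit: 4·(1 + 0.58² − 2·0.58·0.5) = 3.03.
- Pooled over six visits: (0.71 + 5·3.03)/6 = 2.64.
- Reported SE: √(2.64·2/100) = 0.230. Correct SE: √(3.03·2/100) = 0.246.
- Implied rejection: P(|Z| > 1.972·0.230/0.246) ≈ 6.5%, which agrees with the simulation for (c).

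**Simulated rejection (%) of the week-24 contrast under the null, complete data.** There were 40,000 trials per scenario (Monte Carlo SE about 0.1–0.2 points). The row for listed effects with an unstructured covariance used 2,500 (about 0.4 points).

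| Fit | a | b | c |
|---|---|---|---|
| Week 0 as response and covariate, random intercept | 8.2 | 7.7 | 6.5 |
| Same, spatial power | 7.5 | 7.1 | 6.3 |
| Week-0 rows removed, random intercept | 6.2 | 5.9 | 4.8 |
| Same, spatial power | 6.0 | 5.8 | 4.7 |
| Week 0 as response and covariate, unstructured limit (change score) | 3.4 | 2.9 | 3.3 |
| Listed effects only, random intercept | 6.6 | 6.4 | 5.7 |
| Listed effects only, unstructured | 4.1 | 3.8 | 4.4 |
| Week-24 ANCOVA with baseline and strata | 4.9 | 5.0 | 4.9 |

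In (a), the random-intercept fit with baseline used twice reports a mean SE of 0.217 against an empirical SD of 0.248. Then 1.972·0.217/0.248 = 1.73, which implies about 8.4%. Separate simulations with week 0–24 correlations from 0.3 to 0.7 gave 5.7–9.1%.

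**Share due to week 0.** Removing the week-0 rows lowers rejection by 1.3–2.1 points before rounding. Under (a) and (b) the remaining excess comes from the common baseline slope and the homogeneous covariance.

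**Unstructured case.** The week-0 variance is proportional to (1 − slope)², so −2 log L contains 2n·log|1 − slope|. With n = 200, moving the slope from 0.5 to 0.9999 changes it by 400·ln(0.0001/0.5) = −3407. In one fitted data set −2 log L went from 530 to −2877, a drop of 3407. There is no maximum. The limit is the change score:
- SE = 2·√(2(1 − r))·√(2/100), which is 0.283 at r = 0.5 and 0.320 at r = 0.36. Week-24 ANCOVA has 0.246 and 0.265.
- Power for 1 unit is about 94% at r = 0.5. At r = 0.36 it is 87.5%, against about 96% with ANCOVA.

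**Change contrast.** If the endpoint wording led the programmer to test the change from week 0 within the same model, the covariate would cancel. Rejection would be 3.3–5.7% (random intercept) or 1.3–2.6% (spatial power).

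**The case against.** The best defence is that the SAP never writes this model out. Its effect list has no baseline value. The covariate comes from protocol version 4, whereas the SAP names version 5. The SAP Summary speaks of missing data after baseline, which suits a model with post-baseline responses only. The list of weeks could be read as describing data collection. This stands in part: the double use of baseline is one reading of the text and not its only one. But the SAP twice places week 0 in the analysed data and promises baseline adjustment, and nothing in it resolves the two.

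A reader might infer more than the documents support:
- *That week 0 causes the whole 6–9%.* It adds about 1.3–2.1 points.
- *That leaving out the covariate is always liberal.* With the listed effects only, the test is slightly liberal under a random intercept (about 6%), because the pain stratum is itself a cut of FIQ-R pain. The visit schedules first place that questionnaire at week 0, although protocol section 7.3 mentions patient-reported measures in its account of screening. Under an unstructured covariance the rate is about 4%, and the cost is precision (SE about 0.27 against 0.246 in scenario a).
- *That the change-score limit underpowers the trial.* At correlation 0.5 it still has the planned 94%. The SAP's sample size counted on no gain from baseline adjustment.
- *That 128 patients is a dropout forecast.* The SAP uses it as a smaller ITT sample that gives 80% power. It gives no dropout rate.

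A pure random intercept also fits poorly with the SAP's expectation of decaying correlation. A patient effect plus serial correlation gave 7.6/7.0/6.6% in a/b/c, which is still liberal.

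**Conclusion.** The concern holds in conditional form. If baseline is fitted as both response and covariate, no covariance examined gives both the promised adjustment and a 5% test. Random-intercept and spatial-power fits reject about 6–9%. An unstructured fit either fails to converge or becomes a conservative, unadjusted change score. The mechanism is algebraic and certain. The percentages rest on assumed visit correlations and complete data. With an assumed 20% missing at week 24, the first two fits gave 6.2–8.5%. This is more than missing detail, because following the text literally produces one of these faults in the primary analysis.

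**What to change.** Use baseline once, and state that the primary contrast is the group difference at week 24. Either:
1. take weeks 4, 12, 20, 24 and 36 as responses, with group, week, group × week, baseline, baseline × week and the three strata; or
2. use a constrained longitudinal model with week 0 as a response, equal arm means at week 0 and no baseline covariate.

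In both cases name an unstructured within-patient covariance and a fallback if it does not converge. Removing week 0 alone is not enough, as the third and fourth table rows show. For outcomes measured only at weeks 0 and 24 (AMPS, SENS), option 1 is ANCOVA at week 24.

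Option 1 with an unstructured covariance rejected 4.6–4.7% on complete data, with reported SE equal to empirical SD. With 20% missing it gave 4.6–5.0%. Option 2 was not simulated here.

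The change costs a few lines of SAP text and SAS code before unblinding, and no new data. The interval will be somewhat wider than the literal random-intercept fit would report (scenario a: SE about 0.246 instead of 0.217).

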A superiority trial: The hypothesis testing framework of this trial is to assess if CBD is superior to placebo in reducing FIQ-R pain in patients with fibromyalgia when assessed 24 weeks from baseline. The *P*-value will represent the probability of obtaining results as extreme as the ones observed, assuming that the null hypothesis is true (i.e., that there is no difference between groups). A smaller *P*-value indicates stronger evidence against the null hypothesis and will be applied as a threshold for determining statistical significance (1). If the two-sided *P*-value for the primary endpoint is below an α level of 5% ($P<0.05$), we will reject the null hypothesis, suggesting that the observed effect is unlikely to have occurred by random chance alone.

Randomization, allocation concealment and blinding

Stratified randomization was based on permuted blocks of up to 8 individuals; stratification was used to ensure good balance of participant characteristics in each group based on three clinically important factors. A computer-generated randomization sequence was created for each of the 8 eight strata, and consecutively patients enrolled were allocated to the corresponding treatment arms. The randomization sequence was created by an independent biostatistician using a random number generator (SAS Proc Plan), and subsequently entered in the electronic Case Report Form (e-CRF) subdivided by strata, that was developed specifically for the study, by an independent data manager. Investigators, sponsor, and outcome assessors were blinded to the permuted blocking strategy.

Sample size and power considerations

Integral to the structure of a randomized trial is the pre-established calculation of sample size, ensuring that the study is well-positioned to attain its predetermined primary objective with a high likelihood of success. In a randomized trial, the target difference refers to the desired difference between the experimental intervention and control comparator group regarding the outcome being measured (2). We decided that a difference between groups corresponding to one FIQR pain unit would correspond to a Minimal Important Difference in a population of fibromyalgia patients (3).

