Figure 3. Forest plot displaying change from baseline at week 24 in Primary and Key Secondary outcomes using the Standardized mean difference with 95% confidence interval.

Table 3. Harms: Adverse Events in Total and observed in at least 5% of the ITT population.

Appendix Table 2a. Primary and Key Secondary Outcomes at 24 weeks from Baseline, based on the ITT population where missing data is replaced used a single-step non-responder imputation technique for continuous outcomes.

Appendix Table 2b. Primary and Key Secondary Outcomes at 24 weeks from Baseline, based on the Per Protocol population (Repeated Measures Mixed Effects Models)

Figure 1 Trial Profile: Patient flow throughout the trial

[figure not shown]

Table 1. Baseline Characteristics for the Intention-To-Treat Population

Variables	CBD	Placebo	Total
Age, years			
Body Mass Index kg/m ²			
Duration of chronic pain in months			
Tender point count, number			
Pain medication:			
– Weak analgesics (Paracetamol/NSAIDs), n (%)			
– Secondary analgesics (Antidepressants/Anticonvulsants), n (%)			
Expecting a positive effect of the study drug, n (%)			
Marital status:			
– Married / cohabiting, n (%)			
Education:			
– Secondary school (9 th or 10 th grade), n (%)			
– High school, n (%)			
– Bachelor's / Master's degree, n (%)			
Occupation:			
– Working full time, number (%)			
– Working part time with social benefit (Flex job), n (%)			
– Other social transfer income, n (%)			
– Disability pension, n (%)			
– On sick leave, n (%)			
– Pending social welfare application, n (%)			
Primary and Key Secondary Outcomes			
Pain intensity, average last seven days, FIQ NRS 0-10			
Sleep quality, PSQI 0-3			
Sleep duration, PSQI 0-3			
Observed sleep duration SENS, number of minutes			
Observed sleeping patterns, SENS number of awakenings			
Performance-based activities of daily living, AMPS ADL motor ability, Logits			
Performance-based activities of daily living, AMPS ADL process ability, Logits			
Self-reported activities of daily living, ADLQ, Logits			
Quality of life, EQ5D global VAS 0-100			
Energy, FIQ NRS 0-10			

Table 2. Change in Primary and Key secondary endpoints at 24 Weeks from Baseline based on the ITT population (Repeated Measures Mixed Effects Models)

	Change from baseline after 24 weeks of treatment (95% CI)	Difference between groups (95% CI)	P-value
Primary Outcome:	CBD Placebo		
Pain intensity, average last seven days, FIQ NRS 0-10			
Key Secondary Outcomes:			

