12.2 Statistical analyses

The details for the statistical analyses plan (SAP) will be determined prior to the completion of data collection and before the data analyses are initiated [64]. The prespecified efficacy analyses will be based on the data for full analysis set; the intention-to-treat (ITT) population, which includes all participants that are assessed and randomized at baseline. In the case of missing data at week 24, the baseline values will be carried forward and included in the of trial analyses.

The primary analyses will be the comparison between cannabidiol 50 mg and placebo, using a mixed linear repeated-measures ANCOVA model with treatment, stratifying factors, and weeks from baseline as fixed effects; in order to reduce the random variation, we will adjustment for the level at baseline as a covariate. From this model the potential observed differences in pain intensity (FIQ-R NRS) and the secondary continuous outcomes will be estimated together with the associate 95% confidence interval and the p-value corresponding to the test of the hypotheses of no difference between treatments (i.e. the null hypothesis).

To establish the efficacy of cannabidiol 50 mg compared to placebo in patients with fibromyalgia, the key secondary endpoints are tested in a hierarchical manner in the order in which endpoints are presented. Cannabidiol will be considered statically significantly better than placebo with respect to change in pain intensity FIQ-R NRS if the null hypothesis is rejected (p<0.05). Categorical changes for dichotomous end points will be analyzed with the use of logistic regression with the same fixed effects and covariates as

AUTHOR: [name], The Parker Institute, Copenhagen University Hospital

DATE: 2020-12-14

Protocol number P142; Version: 4; EudraCT: 2019-002394-59, Regional Ethical Committee Journal Number H-20047715. ClinicalTrials.gov Identifier:

the respective ANCOVA for continuous outcomes (see above). Sensitivity analyses will be performed to assess the robustness for the primary analyses, including a 'non-responder imputation', 'multiple imputation techniques ', and a 'per protocol analysis'.

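### Do the responder analyses need covariate adjustment, and a stated interval method for the risk difference and NNT?

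*SAP*

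**What the plan says.** The SAP, Analysis methods, defines responders at week 24 by an improvement of more than one unit, 30% or 50% in FIQ-R pain, and states: "For these dichotomous outcomes, we will calculate the Risk Ratio (RR) with 95 % CI comparing the two groups". The next sentence says that "the RR values might be converted into Risk Differences (RD) and Number Needed to Treat (RD"), where the last abbreviation should be NNT. Missing binary outcomes count as non-response (SAP, Missing Data), so each denominator is the full ITT arm.

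The SAP's Table 2 is titled "Change in Primary and Key secondary endpoints at 24 Weeks from Baseline based on the ITT population (Repeated Measures Mixed Effects Models"). Its responder rows, labelled n (%), fall under the column "Difference between groups (95% CI"), and no RR column is visible.

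Three other statements bear on this:
- On randomisation, the SAP says "A computer-generated randomization sequence was created for each of the 8 eight strata".
- On the mixed models, it says "All between-groups differences will be adjusted for baseline level to reduce random variation".
- Protocol version 4, section 12.2, had planned that "Categorical changes for dichotomous end points will be analyzed with the use of logistic regression with the same fixed effects and covariates" as the ANCOVA, and also said "The details for the statistical analyses plan (SAP) will be determined prior to the completion of data collection". The SAP's title page cites protocol version 5, which is not among the documents.

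**The concern.** Three things look wrong on a first reading.

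1. **Adjustment.** Allocation was stratified by sex, age and pain, the continuous outcomes are adjusted for baseline, and protocol version 4 planned adjusted logistic regression. A crude RR seems to discard that information and to step back from the protocol.
2. **Interval.** The text promises an RR, while the table shell asks for a difference with an interval under a title that names only mixed models. If the RR limits were turned into RD limits with the placebo risk held fixed, the interval would ignore the uncertainty in that risk, and the NNT limits would inherit the fault. The SAP Summary says the responder analyses are there to ease interpretation, so NNT is a figure clinicians may quote.
3. **Definitions.** SAP Outcome definitions lists two responder categories, whereas the Summary, Analysis methods and Table 2 use three. Table 2 uses ≥ for 30% and 50%; protocol version 4, section 9.2, says more than.

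**Working it through.** **The plan's own figure.** The only power figures in the documents concern the primary outcome (SAP, Sample size and power considerations): difference 1, SD 2, two-sided 5%. The noncentrality is 1 / (2 × √(2/n)), with n per arm.
- n = 100: 3.536, power 0.940, against the stated 94%.
- n = 64: 2.828, power 0.80, against the stated 80%.

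Neither document gives responder rates, so everything on responders below rests on assumptions.

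**Validity of the crude RR.** Trials of 200 patients were simulated with permuted blocks of 4, 6 or 8 in eight strata. Assumptions: 8% male, 40% under 45, baseline pain about N(6.8, 1.6) rounded and kept to 4–10, week-24 SD 2, placebo change -1, sex and age not prognostic, correlation of baseline with week 24 of 0.3, 0.5 or 0.7, and dropout 0 or 20% counted as non-response. Type I error of the crude log-RR test was 2.9 to 5.2%. A second set (baseline N(6.5, 1.8), 10% male, 15% missing, correlation 0.2 to 0.6) gave 3.1 to 5.6%. The test is at or slightly below nominal, as expected when stratification is ignored.

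**Gain from adjusting.** Power at a 1-point effect in the first set, crude against standardised logistic with a Mantel-Haenszel fallback:

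| Index | Correlation 0.3 | 0.5 | 0.7 |
|---|---|---|---|
| >1 unit, no dropout | 73.2 vs 78.3% | 85.8 vs 87.5% | 97.2 vs 97.2% |
| >1 unit, 20% dropout | 57.0 vs 60.1% | 69.1 vs 69.8% | 86.9 vs 86.4% |

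For ≥30% and ≥50% the change was -1.4 to +1.5 points. In the second set, adjusted by a modified Poisson model, the gain was 0.3 to 4.8 points. A Mantel-Haenszel analysis over the eight strata, against crude, gave about -1.3 to +3.1 points.

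**Cost of adjusting.** With few men, the sex term cannot be estimated when no man responds. For ≥50% the logistic model failed in 3.8 to 12.1% of trials at a 1-point effect and 11.9 to 35.8% at no effect. These rates depend on the assumed placebo change. With 8% male and response probability p, the chance that no man responds is (1 - 0.08p)^200. At p = 3.7%, 11.1% and 25.7% (placebo change 0, -1 and -2) that is about 55%, 17% and 2%.

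**RD by conversion: the point.** p0 × (RR - 1) = p0 × (p1/p0 - 1) = p1 - p0, so the point conversion is exact at the observed placebo risk. For 45 vs 30 per 100: 0.30 × (1.50 - 1) = 0.15, NNT = 1/0.15 = 6.7.

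**RD by conversion: the interval.** With 100 per arm:
- Direct: p1 - p0 ± 1.96 × √(p1(1-p1)/100 + p0(1-p0)/100).
- Converted: p0 × (RR limit - 1), with RR limits exp(log RR ± 1.96 × √(1/x1 - 1/100 + 1/x0 - 1/100)).

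| CBD vs placebo | RR (95% CI) | Direct RD, points | Converted RD, points | Width ratio |
|---|---|---|---|---|
| 61 vs 39 | 1.56 (1.17 to 2.09) | 8.5 to 35.5 | 6.6 to 42.6 | 1.33 |
| 45 vs 30 | 1.50 (1.04 to 2.17) | 1.7 to 28.3 | 1.1 to 35.1 | 1.28 |
| 20 vs 10 | 2.00 (0.99 to 4.05) | 0.2 to 19.8 | -0.1 to 30.5 | 1.57 |
| 38 vs 39 | 0.97 (0.69 to 1.38) | -14.5 to 12.5 | -12.2 to 14.9 | 1.01 |
| 20 vs 30 | 0.67 (0.41 to 1.09) | -21.9 to 1.9 | -17.8 to 2.8 | 0.86 |

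Converted limits are usually too wide when CBD does better, and can be wider or narrower when RR is below 1. At placebo risks of 20 to 40% and RD of 10 to 15 points their coverage was 98.0 to 99.0%, against 94.6 to 95.1% for a Newcombe interval. A converted interval excludes 0 exactly when the RR interval excludes 1, so it cannot contradict the measure the SAP specifies.

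**The case for a change.** The strongest case is that the SAP exists to remove analyst choice, and here a choice is left. The text gives an RR that has no visible column, and the table gives a difference with no stated method. Borderline results can differ: at 20 vs 10 the direct RD interval excludes 0 and the converted one does not. Adjustment can also help more than the tables above suggest. If sex and age each shifted week-24 pain by 1 point (correlation 0.3, >1 unit, trials where the model fitted), power would be 72.1% crude and 79.0% adjusted. The operator also matters on an integer scale: at correlation 0.5 and a 1-point effect, 50% responders are 25.8 vs 11.2% with ≥ and 17.4 vs 6.6% with >.

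Part of this stands: the RD interval method is not named, and the table heading does not fit the responder rows. The rest carries less weight.
- The SAP mentions converting RR values as an option and says nothing about converting limits. With n (%) in each arm, the direct interval is the obvious choice and any reader can compute it.
- The table is an empty shell built for continuous rows, and its header is broken in the text available, so its layout is weak evidence.
- The 6.9-point gain needs two strong prognostic factors that the documents do not suggest.
- Version 4 left the details to the SAP and is not the version the SAP cites, so no departure is shown. The same applies to its more than wording, and Table 2 of the SAP states its operators.

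**Conclusion.** No change follows. The specified analysis, a two-group RR with 95% CI under non-responder imputation, is valid. Adjustment is a fair trade-off: over the main settings tried it moved power by -1.4 to +5.1 points, in return for a model that may not fit for the 50% index and would need a fallback rule. The unnamed RD interval is a gap that an analyst fills sensibly from the two proportions, with NNT as 1/RD. It would do harm only under a conversion of limits that the SAP does not state. The two-against-three category count, the NNT label and the Table 2 heading are clerical.

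The responder indices are secondary, and the primary analysis of pain is unaffected. The exact-count comparisons need no assumption beyond 100 per arm. The power, error and model-failure figures depend on assumed response rates, correlation, dropout, sex split and a placebo change of about -1. Other values would move them, most of all the failure rate for the 50% index.
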